9.6.1.1 Phase 2 Cohort

In the Phase 2 Cohort, efficacy endpoints will be collected during the Base and Extension Periods. For the Base Period, the analysis timepoint of interest is Week 12. For the Extension Period, the analysis timepoint of interest is Week 24. Summary statistics will be provided for every planned data collection timepoint described in the SoA (Section 1.3).

Primary Endpoint

Following the ICH E9 (R1) guidance [European Medicines Agency 2020], The primary estimand for the primary objective used for the Phase 2 Cohort contains 5 attributes:

• The treatment condition of interest is MK-5475 or matching placebo with stable concomitant PAH-specific therapy, as defined in Section 5.1.

- The population of participants targeted by the clinical question are male/female participants with PAH between the ages of 18 and 75 years (inclusive).
- The variable to address the clinical question is PVR at Week 12.
- The following are intercurrent events, along with the approaches to handle them:
 - Death: hypothetical strategy to evaluate PVR at Week 12 as though death would not occur.
 - Treatment discontinuation: treatment policy strategy seeking to use every participant's actual Week 12 value, regardless of whether they are still taking study medication.

The approach to handling missing data for these intercurrent events is described below.

• The population-level summary is mean percent change from baseline in PVR at Week 12.

For this estimand, the primary approach will use a robust regression method to address the primary hypothesis. Robust regression method will be used because percent change from baseline in PVR is not expected to follow a normal distribution, based on other Phase 2 clinical trials which have used non-parametric methods for analyzing PVR [Simonneau, G., et al 2012] [Ghofrani, H. A., et al 2010]. The robust regression model will include terms for treatment and WHO-FC (Class II and Class III/IV). Missing PVR observations at Week 12 from participants in all treatment groups will be imputed following a PMM. Missing data due to death will be imputed as the worst outcome among all observed data. Missing data due to treatment discontinuation will be imputed based on the observed PVR observations at Week 12 from the placebo group referred as J2R (detailed below). If there are missing Week 12 data for other reasons, J2R will also be used. The randomization seed for imputations will be 5475007.

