The difference (MK-5475 minus placebo) in percent change from baseline and the associated 95% CI and *p*-value will be provided. A *p*-value for the comparison of MK-5475 versus placebo <0.025 (one-sided) will be considered statistically significant contingent upon the multiplicity strategy (Section 9.8).

The following steps will be taken to perform the primary analysis, including imputation for missing data. Percent change from baseline in PVR at Week 12 is the response variable:

- 1. Define imputation model for different missingness patterns:
 - a. Obtain the worst outcome among all observed data.
 - b. Within the placebo group, for participants with both baseline and Week 12 data, fit an ANCOVA model including terms for treatment and WHO-FC (Class II and Class III/IV).

- 2. Impute missing data for different missingness patterns:
 - a. Death: for participants (in both treatment groups) who died before Week 12, the worst outcome among all observed data will be used to impute the missing Week 12 values.
 - b. Reasons other than death: For participants (in both treatment groups) missing the response variable, the fitted model in Step 1 will be used to impute the missing values.
- 3. Robust regression based on a Huber-type M estimator [Huber, P. J. 1973] will be performed for the imputed dataset. The model will include terms for treatment and WHO-FC (Class II and Class III/IV).
- 4. Steps 2 and 3 will be repeated 50 times to create 50 complete datasets and 50 sets of parameter estimates.
- 5. The final parameter estimate for the mean percent change will be the average of the 50 parameter estimates for the mean percent change from Step 4.
- 6. Steps 1 through 5 will be repeated 200 times based on bootstrap resampling. The resulting standard error for the mean percent change will be the standard error of the resulting parameter estimates obtained in the 200 bootstrap resampled datasets. The CI and *p*-value will be derived from a normal distribution based on the final parameter estimate and its standard error.

Two sensitivity analyses for percent change from baseline in PVR will be performed to assess the impact of missing data imputation. Within the same PMM structure in the primary analysis, for missing data due to reasons other than death, 1 analysis will use a tipping point approach and the other analysis will use an approach referred to as washout imputation.

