The difference in change from baseline and the associated 95% CI and *p*-value will be provided (MK-5475 minus placebo). A *p*-value for the comparison of MK-5475 versus placebo <0.025 (one-sided) will be considered statistically significant.

The following steps will be taken to perform the primary analysis, including imputation for missing data. Percent change from baseline in 6MWD at Week 12 is the response variable:

- 1. Define imputation model for different missingness patterns:
 - a. Obtain the worst outcome among all observed data.
 - b. Within the placebo group, for participants with both baseline and Week 12 endpoint, an MMRM model including terms for treatment and WHO-FC (Class II and Class III/IV) will be fit.
- 2. The same procedure in Steps 2 through 6 described in Section 9.6.1.1 will be used for analysis.

Two sensitivity analyses of the estimand for change from baseline in 6MWD will be performed to assess the impact of missing data imputation. Within the same PMM structure in the primary analysis, for missing data due to reasons other than death, 1 analysis will use a tipping point approach and the other analysis will use an approach referred to as washout imputation. The analysis approaches are the same as in the 2 sensitivity analyses described in Section 9.6.1.1 except the missing data due to reasons other than death will be imputed by the MMRM model in the primary analysis.

As a supplemental analysis, the primary analysis will be repeated, excluding participants who participated in the Phase 2 Cohort.

Secondary Endpoint

The primary approach for addressing the mean change from baseline in 6MWD at Week 24 will use the same robust regression method in Section 9.6.1.1. Summary statistics will be provided for the proportion of participants whose WHO-FC is not worse at Week 12 relative to baseline. Table 6 summarizes the analysis strategy for efficacy endpoints in the Phase 3 Cohort.

Endpoint	Туре	Statistical Method	Analysis Population	Missing Data Approach
Primary Endpoint				
Change from baseline in 6MWD at Week 12	P Sen Sen	RR RR RR	FAS FAS FAS	PMM-J2R PMM-Tipping point PMM-Washout
Secondary Endpoints				
Change from baseline in 6MWD at Week 24	Р	RR	FAS	PMM-J2R
Proportion of participants whose WHO functional class does not worsen at Week 12 relative to baseline.	Р	SS	FAS	N/A

Table 6	Analysis Strategy for Primary and Secondary Efficacy Endpoints in the Phase
	3 Cohort

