9.9.1 Efficacy

Phase 2 Cohort

08P53K

The study design assumptions are based on results from other Phase 2 clinical trials in the literature for PAH participants with similar design. In the Phase 2 study assessing selexipag, the observed mean percent change from baseline PVR was 33% with standard deviation 0.34,

and the overall study completion rate was 91% [Simonneau, G., et al 2012]. Comparable results were reported in a Phase 2 study assessing riociguat [Ghofrani, H. A., et al 2010].

Through 12 weeks post-randomization, drop-out is expected to be approximately 10% in each treatment group. However, based on the approach to missing data, all randomized participants per group are expected to be included in the primary analysis and are the basis for sample size and power calculations, accounting for imputation of missing data.

Power and sample size are based on the percent change from baseline in PVR at Week 12. Assuming the true percent change from baseline in PVR at Week 12 is -30% for each MK-5475 dose versus 0% for placebo, the assumed percent change from baseline in PVR at Week 12 using J2R to impute missing data would be 27% for each MK-5475 dose versus 0% for placebo. The assumed standard deviation of the difference of percent change from baseline in PVR at Week 12 between each MK-5475 and placebo is 0.4. Under these assumed percent change and standard deviation, a sample size of 41/group provides more than 85% power (approximately 86.4%) to demonstrate superiority for each of the MK-5475 treatment comparisons using a one-sided alpha=0.025.

With respect to the secondary endpoint of change from baseline in 6MWD at Week 12, a sample size of 41/group will provide a half-width of the 95% CI to be 30 meters, assuming the standard deviation of the change from baseline in 6MWD is 70.

Phase 3 Cohort

The study design assumptions are based on results from Phase 3 PAH clinical studies in the literature with similar design [Ghofrani, H. A., et al 2013] [Galie, N., et al 2008] [Galie, N., et al 2005] [Rubin, L. J., et al 2002]. A clinically relevant increase in 6MWD (>30 meters) correlates with improved clinical outcomes in PAH (Section 4.2.1.1).

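### With only 200 bootstrap resamples, the primary standard error carries about 5% Monte Carlo error, so a borderline verdict depends on the arbitrary resampling draw

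*Combined protocol and SAP*

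**What the plan says.** Section 9.6.1.1 sets out the Phase 2 primary analysis in six steps. Within each dataset, "Steps 2 and 3 will be repeated 50 times to create 50 complete datasets and 50 sets of parameter estimates", and Step 5 averages them. Step 6 supplies the variance: "Steps 1 through 5 will be repeated 200 times based on bootstrap resampling", and the spread of the estimates across those resamples is taken as the standard error. The interval and p-value "will be derived from a normal distribution based on the final parameter estimate and its standard error". No analytic standard error stands behind this one.

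Section 9.6.1.2 carries the method into the Phase 3 primary analysis: "The same procedure in Steps 2 through 6 described in Section 9.6.1.1 will be used for analysis". The resample count of 200 therefore applies there too.

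On reproducibility, Section 9.6.1.1 says "The randomization seed for imputations will be 5475007", and Section 9.6.1.2 gives the same seed. Neither section says whether it also drives the bootstrap draws. The documents give no reason for choosing 200, no convergence check and no rule for borderline results.

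**The concern.** A bootstrap standard error is itself an estimate, and its precision depends on the number of resamples. With 200, the denominator of the test statistic moves by several per cent from one set of draws to another while the trial data stay fixed. Far from the threshold this is harmless. Near it, the draw can decide which side the p-value falls on.

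Three decisions use this statistic: the Phase 2 interim comparison (taking the interim to use the primary method), each step of the descending dose sequence in Section 9.8, and the single confirmatory Phase 3 test. In the dose sequence, a failure at 380 µg caused by simulation noise would also close testing of the two lower doses. The tipping-point analysis looks for the shift at which significance is lost. If it uses the bootstrap standard error, it is read exactly where the noise matters most.

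**Working it through.** **Inputs.** From Section 9.6.1.1: B = 200 resamples, 50 imputations and a normal reference distribution. From Section 9.9.1, after jump-to-reference imputation: Phase 2 difference 27 points, SD 40 points, 41 per group; Phase 3 difference 27 m, SD 70 m, 143 per group; one-sided alpha 0.025. From Section 4.1: interim at about 120 participants.

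**1. Reproduce the plan's power.** The mean of z is difference / (SD × √(2/n)).
- Phase 2: 27 / (40 × √(2/41)) = 3.06. Power is 86.35%, against the stated 86.4%.
- Phase 3: 27 / (70 × √(2/143)) = 3.26. Power is 90.3%, against the stated 90%.

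**2. Reconstruct the interim.** The spent alpha is redacted, so it is an assumption here. With t = 120/164 = 0.732, the spending function in Section 9.7 gives 2 − 2Φ(2.241/√0.732) = 0.0088, a critical z of 2.37. With 30 per group, the mean of z is 0.27 / (0.4 × √(2/30)) = 2.61. Applying the same 10% dilution to each effect in Table 8 gives 59.5%, 75.0%, 86.7%, 93.9% and 97.6%. All five match the table, so the assumption is well supported.

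**3. Monte Carlo error of the standard error.** For near-normal bootstrap estimates, the squared ratio of the reported to the converged standard error follows χ²(B−1)/(B−1). The coefficient of variation is 1/√(2(B−1)) = 1/√398 = 5.0%. A small simulation of the plan's algorithm (jump-to-reference, 50 imputations, Huber fit, 41 per group, 10% missing) gave 4.8%. In 95% of draws the reported standard error lies between 0.902 and 1.098 times its converged value.

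**4. Effect on a borderline p.** At a converged z of 1.96, the reported z runs from 1.96/1.098 to 1.96/0.902, so p runs from 0.037 down to 0.015. A converged p of 0.022 is declared significant in 72% of draws, and one of 0.028 in 32%.

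**5. Average over trials.** Integrating over the distribution of z gives the chance that a single run differs from the converged verdict:

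| Scenario | B = 200 | B = 2,000 |
|---|---|---|
| Phase 3 design effect | 1.3% | 0.4% |
| Phase 2 top dose, design effect | 1.7% | 0.5% |
| Phase 2 interim, design effect | 3.7% | 1.2% |
| Null, threshold 0.025 | 0.5% | 0.1% |

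At B = 200 the overall type I error is 2.57% against 2.50%. Phase 2 power is 86.29% against 86.35%, and Phase 3 power 90.28% against 90.35%.

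**6. With 2,000 resamples.** The coefficient of variation is 1/√3,998 = 1.6%, and at a converged p of 0.025 the 95% range is 0.022 to 0.029.

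**The case against.** The strongest reply is that nothing here is invalid. Step 6 can be executed as written, error control is essentially intact, and the choice between 200 and 2,000 is one of precision. That stands, and it limits the priority.

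A reader might infer that simply rerunning the analysis could reverse the verdict. The documents do not support that. A seed is prespecified, and because Step 6 repeats the imputation steps, it already operates inside the bootstrap loop. If it also governs the resampling, the same program on the same data in the same order returns the same answer. Its scope is unstated, so this is an ambiguity and not evidence of irreproducibility. A fixed seed makes a run repeatable, however; it does not make the standard error accurate.

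A reader might also count how often two independent runs disagree (1.9%, 2.4% and 5.2% for Phase 3, Phase 2 top dose and interim). The trial reports one run, so comparison with the converged verdict is the relevant measure, and it gives the smaller figures in the table.

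Nor does this standard error alone settle the interim. Section 4.1 makes futility nonbinding and stopping optional, an external committee reviews the results, and dose selection weighs efficacy and safety together. The scenario with the largest percentage is thus the one least tied to a single p-value. The strictest consequence is in Phase 3, where the rate among the design-effect scenarios is lowest.

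**Conclusion.** The point holds as one of avoidable imprecision. The primary standard error in both cohorts carries about 5% Monte Carlo error, and converged p-values between about 0.016 and 0.039 have at least a 2.5% chance of being reported on the other side of 0.025. The documents do not support a claim of a biased or invalid test: type I error rises by about 0.07 of a percentage point and power changes by less than 0.1 point.

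The figures assume near-normal bootstrap estimates (supported by the simulation), the design effects and SDs of Section 9.9.1, a threshold of 0.025 at the Phase 2 final analysis (the exact value may be slightly lower once interim alpha is spent), and the reconstructed interim of 30 per group with alpha of about 0.0088. Using 50 imputations adds a smaller error to the point estimate, about 3.6% of one standard error in the simulation, which is not included in these figures. Priority is low to moderate.

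**What to change.** In Step 6 of Section 9.6.1.1, replace 200 with at least 2,000 resamples, and state that this applies to the primary analyses of both cohorts and to the Phase 2 interim. State that seed 5475007 also covers the bootstrap draws, or give a second seed for them. The documents do not give a resample count for the tipping-point and washout analyses; use the same count there wherever they rely on the bootstrap standard error.

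The computing load is 2,000 × 50 = 100,000 robust fits per analysis on at most 286 rows, against 10,000 now, and it is repeated for each shift in the tipping-point range. Because this changes a method for the primary hypotheses, the opening of Section 9 requires a protocol amendment before any unblinding. It need not be an amendment of its own. The estimand, sample size and visits are unaffected. Making the change in advance also avoids the appearance of a post hoc choice if a p-value near 0.025 is later reported.

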3 HYPOTHESES, OBJECTIVES, AND ENDPOINTS

This study will be carried out in 2 parts, a Phase 2 dose selection cohort and a Phase 3 confirmatory cohort. Each cohort includes a Base Period and an Extension Period.

In men and women aged 18 to 75 years (inclusive) with pulmonary arterial hypertension (PAH):

Primary Objectives	Primary Endpoints
 Phase 2 Cohort – to evaluate the effect of MK-5475 versus placebo on the pulmonary vascular resistance (PVR) at Week 12. Hypothesis: at least one MK-5475 dose is superior to placebo in reducing PVR from baseline at Week 12. 	PVR (centrally assessed)
 Phase 3 Cohort – to evaluate the effect of MK-5475 versus placebo on 6-minute walk distance (6MWD) at Week 12. Hypothesis: MK-5475 is superior to placebo in increasing 6MWD from baseline at Week 12. 	6MWD
Secondary Objectives	Secondary Endpoints
Phase 2 Cohort - to evaluate the effect of MK-5475 versus placebo on 6MWD at Week 12.	6MWD
Phase 2 Cohort - to evaluate the effect of MK-5475 versus placebo on hemodynamic parameters other than PVR at Week 12.	-Mean right arterial pressure (mRAP) -Cardiac index -Stroke volume index (SVI)
Phase 3 Cohort – to evaluate the effect of MK-5475 versus placebo on 6MWD at Week 24.	6MWD
Phase 3 Cohort - to evaluate the effect of MK-5475 versus placebo on the WHO functional PAH class at Week 12.	WHO functional class

Phase 2 and Phase 3 Cohorts (independently) – to evaluate the safety and tolerability of MK-5475.	-Adverse Events (AEs)-Discontinuation of study intervention due to AEs
CCI	

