Based on all the considerations, the top dose selected for the Phase 2 Cohort of this study is 380 μ g. A low dose of 32 μ g is selected for evaluation in the Phase 2 Cohort, to expand the exposure-response dataset that can be used to inform dose selection for the Phase 3 Cohort and for future studies and to define a minimally efficacious dose. The 32 μ g inhaler formulated for the Phase 2/3 study is the lowest feasible strength that can be developed using a conventional formulation. The mid dose of 100 μ g is selected for evaluation in the Phase 2 Cohort based on minimal overlap of plasma exposures from that at the high dose at 380 μ g and the low dose at 32 μ g.

Participant response to the 3 different doses of MK-5475 ($32 \mu g$, $100 \mu g$, and $380 \mu g$) will be assessed in the Phase 2 Cohort Base Period. Of these, the treatment dose that shows the best efficacy, as assessed by pulmonary vascular hemodynamics, no evidence of clinically meaningful systemic hypotension, and overall favorable safety profile will be selected for the subsequent Phase 3 Cohort.

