9.6 Statistical Methods

Statistical testing and inference for safety analyses are described in Section 9.6.2. Efficacy results that will be deemed to be statistically significant after consideration of the Type I error control strategy are described in Section 9.8. Nominal *p*-values for secondary endpoints may be provided as an assessment of strength of evidence without intent to make inferential claims. All statistical tests will be conducted at the α =0.025 (one-sided) level.

For analysis purposes, the baseline assessment is considered the one closest to but before or on the day of randomization (Day 1).

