In the tipping point approach, missing values due to reasons other than death will be imputed based on the first step in the primary analysis with a positive adjustment Δ added for the MK-5475 group. The inference will be carried out for a range of values of Δ . The smallest value of Δ that renders the significant result into a non-significant result will be the tipping point value, which provides a measure of robustness of the primary result.

In the washout imputation approach, missing values due to reasons other than death in the MK-5475 group will be imputed from a normal distribution with the expected value set to the baseline value in the MK-5475 group and standard deviation computed based on the root mean squared error from the ANCOVA model described in the primary analysis. Missing values in the placebo group will be imputed in the same way as in the primary analysis.

Secondary Endpoint

The primary approach for addressing the mean change from baseline in 6MWD at Week 12 will use the same robust regression method described above for the primary endpoint. Summary statistics will be provided for other selected hemodynamic parameters listed in

Section 9.4.1. Table 5 summarizes the analysis strategy for efficacy endpoints in the Phase 2 Cohort.

Endpoint	Туре	Statistical Method	Analysis Population	Missing Data Approach
Primary Endpoint				
Percent Change from baseline in PVR at Week 12	P Sen Sen	RR RR RR	FAS FAS FAS	PMM-J2R PMM-Tipping point PMM-Washout
Secondary Endpoints				
Change from baseline in 6MWD at Week 12	Р	RR	FAS	PMM-J2R
Change from baseline in selected hemodynamic parameters at Week 12	Р	SS	FAS	N/A

Table 5Analysis Strategy for Primary and Secondary Efficacy Endpoints in the Phase
2 Cohort

6MWD=6-minute walk distance; FAS=full analysis set; J2R=jump-to-reference; N/A=not applicable; P=Primary PMM=pattern mixture model; PVR=pulmonary vascular resistance; RR=robust regression; Sen=Sensitivity; SS=summary statistics.

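### Phase 2 mRAP, cardiac index and SVI: the objective is an effect versus placebo, but the plan commits only to summary statistics

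*Combined protocol and SAP*

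**What the plan says.** Section 3 (and the Synopsis) sets a Phase 2 secondary objective "to evaluate the effect of MK-5475 versus placebo on hemodynamic parameters other than PVR at Week 12", with mRAP, cardiac index and SVI as its endpoints. Section 9.4.1 lists the mean change from baseline in each at Week 12.

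For their analysis, Section 9.6.1.1 says that "Summary statistics will be provided for other selected hemodynamic parameters listed in" Section 9.4.1. The Table 5 row "Change from baseline in selected hemodynamic parameters at Week 12" shows method SS, population FAS and missing-data approach N/A.

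The other Phase 2 secondary efficacy endpoint, 6MWD at Week 12, is treated differently: its analysis "will use the same robust regression method described above for the primary endpoint". For PVR that method yields "The difference (MK-5475 minus placebo) in percent change from baseline and the associated 95% CI" and a p-value. Table 5 gives 6MWD the entry RR with PMM-J2R.

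On dose choice, Section 4.3 looks for "the treatment dose that shows the best efficacy, as assessed by pulmonary vascular hemodynamics", together with the hypotension and general safety findings. Section 4.2 says that the team will look at all Base Period safety and efficacy information first.

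**The concern.** An objective worded as an effect against placebo needs an estimate of that effect and a statement of its precision. For these three endpoints the plan promises neither. Summary statistics listed against SS, next to rows that name a regression, read most naturally as tables by treatment group, although the text does not say so outright.

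The endpoints are not idle. Section 4.2.1.1 counts right atrial pressure and cardiac index among the hemodynamic measures that help to define dose-response, so they are likely to be looked at when the Phase 3 dose is chosen. Without a stated contrast and interval, a difference between group means can be given more weight than its precision supports. Without a missing-data rule, it is also unclear whom the means describe. For these endpoints the FAS in Section 9.5.1 asks for only one observation, at baseline or later, so it admits participants for whom no change from baseline can be computed.

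**Working it through.** **Is the contrast promised elsewhere?**
- Section 9.6: of nominal p-values it says that "values for secondary endpoints may be provided as an assessment of strength of evidence without intent to make inferential claims". This is optional, names no model and gives no effect estimate.
- Section 9.6.1: it covers methods for the primary and secondary objectives, and sends methods for exploratory objectives to the sSAP.
- Section 9 (opening): later changes to non-confirmatory analyses can be recorded in the sSAP. That is a route to close the gap, not evidence that it is closed.
- Section 9.6.2.1: between-group 95% CIs are planned for specific AEs seen in at least 4 participants in any group, so the plan uses nominal intervals elsewhere, but not for these efficacy endpoints.

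No section commits to a contrast, an interval or a missing-data rule for mRAP, cardiac index or SVI.

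**Inputs (all Section 9.9.1).** 41 per group; PVR difference 27 percentage points after J2R, SD 0.4, one-sided alpha 0.025; 6MWD SD 70 m; drop-out about 10% per group. The documents give no SD for mRAP, cardiac index or SVI, so precision is expressed in SD units.

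**Reproducing the plan's own figures.**
- √(2/41) = 0.2209.
- PVR power = Φ(0.27 / (0.4 × 0.2209) − 1.96) = Φ(3.056 − 1.96) = Φ(1.096) = 86.35%. The plan states about 86.4%.
- 6MWD half-width = 1.96 × 70 × 0.2209 = 30.3 m. The plan states 30 m.

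Both agree, so the same formula can be used for the three endpoints.

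**Precision of a difference from placebo, in SD units: 1.96 × √(2/n).**

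| Participants per group with data | Half-width of 95% CI for the difference |
|---|---|
| 41 | 1.96 × √(2/41) = 0.43 SD |
| 37 (41 × 0.9 = 36.9) | 1.96 × √(2/37) = 0.46 SD |
| 30 (assumption: about 120 at the interim analysis, Section 4.1, split evenly over four groups) | 1.96 × √(2/30) = 0.51 SD |

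A single group mean at n = 41 has half-width 1.96/√41 = 0.31 SD. Intervals around group means would therefore look narrower than the interval for the effect that the objective asks about.

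**The case against.** The strongest reply is that the main hemodynamic measure is fully covered. PVR is the primary endpoint. Each dose gets a difference from placebo with a 95% CI and p-value, ordered testing (Section 9.8) and two missing-data sensitivity analyses; 6MWD gets the robust regression; and Section 9.7 allows MCP-Mod to support dose finding. This stands. A reader might infer that the Phase 3 dose would be picked by comparing raw group means by eye with no measure of uncertainty. The documents do not support that: Section 4.3 does not make mRAP, cardiac index or SVI decisive, and much of the interim detail in Section 9.7 is not visible, so nothing should be built on it.

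A reader might also infer that dropouts are silently removed. The text says only N/A. Section 8.11.5 brings participants who stop treatment in the Base Period back for all Week 12 procedures, so the figure of 37 assumes that the whole 10% drop-out lacks a Week 12 catheterization. Handling is unspecified; it is not shown to be deletion.

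The choice may also be deliberate. No hypothesis is attached to these endpoints, no key secondary endpoints are named, and Phase 3 WHO-FC, another versus-placebo secondary, is likewise SS with N/A in Table 6. 6MWD has more reason for a model, being the Phase 3 primary endpoint. That explains a lower tier, but a lower tier can still carry a nominal interval, and the objective is still comparative.

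Finally, tables with n, mean and SD would let a reader derive an unadjusted interval, and 0.43 SD is what any endpoint would have at this sample size. Both points are fair. The derived interval would lack the stratum term and a defined denominator, and the plan would still not have committed to it.

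**Conclusion.** The point holds as an estimation gap of modest weight. The plan states a comparative objective for three endpoints and commits to no comparative estimate, interval or missing-data rule for them. Type I error is not affected, because these endpoints carry no confirmatory claim. Nor do the documents show that dose selection would go wrong, because PVR has a formal comparison and these parameters are supporting inputs.

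The unreported uncertainty is about 0.43 SD either side of a difference from placebo with 41 per group, and 0.46 SD with 37. These figures assume equal SDs in the two groups, a normal-theory interval and no gain from covariate adjustment. They cannot be put into clinical units from the documents, and no effect on the dose choice can be quantified.

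**What to change.** In Section 9.6.1.1 and the Table 5 row for these parameters, replace SS with each dose-minus-placebo difference in change from baseline at Week 12 and a nominal 95% CI. The model should contain treatment and WHO-FC stratum; the existing robust regression will serve. Label the results non-confirmatory.

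Replace N/A with one of two stated rules:
- participants with both a baseline and a Week 12 value, with the number shown by group; or
- the PVR imputation, with the direction of the worst outcome defined for each parameter. Copying PMM-J2R across without this would not be sound, because an adverse change need not point the same way in all three.

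Intervals against placebo do not show the uncertainty between doses. If dose-to-dose differences in these parameters are to be discussed, their intervals should be given as well.

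The cost is SAP wording, a little extra programming and one more table. Sample size, alpha and trial conduct are unchanged.
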